7 STUDY ADMINISTRATION

7.1 Treatment Assignment Methods

7.1.1 Randomization

Subjects will be randomly assigned to one of the two groups (BioStream training group, or alternate game group) as an ongoing process throughout enrollment.

7.2 Data Collection and Management

See page 8 and pages 19-20 for information on data collection and management.

7.3 Confidentiality

All written or electronic forms (except Informed Consent Forms and Assent Forms) will employ a unique alphanumeric identifier; in no case will the participant's name or other identifying information appear on these forms. The user ID for the BioStream Training and alternate game shall use the same unique alphanumeric identifier. The study team will accomplish this on all parent/guardian or teacher or therapist questionnaires (as applicable) which have lines for child and parent name by applying a label with unique alphanumeric identifier and instructing parents/guardians or teacher or therapist to use generic labels (e.g., biological mother) rather than writing their names. The PI will keep a master list containing PHI and subject ID number separate from coded data forms, which will be maintained in a locked file drawer, cabinet or lock box in the PI's office. Only the PI will have access to this location. The master list will be maintained on a separate password-protected computer and be stored in an encrypted password protected file. Video recordings will stored on password-protected and/or encrypted data storage devices including computers, external hard drives, and/or flash drives only accessible by members of the study team including the Sponsor's study team members. Any member of the study team or third party with HIPPA compliant policies and procedures, blinded to the study group of each subject, may engage in in video recording annotation including therapist practitioners or research organizations. The Sponsor may collect and store all de-identified data on password-protected and/or encrypted data storage devices including computers, external hard drives, and/or flash drives.

7.4 Regulatory and Ethical Considerations

7.4.1 Data and Safety Monitoring Plan

The PI will periodically review the data collection and storage practices associated with this study and determine whether changes to enhance confidentiality and privacy are required. The PI will frequently monitor the quality control of the data with staff and research assistants.

7.4.2 Risk Assessment

Use of BioStream Training or Alternate Game: The tasks associated with use of the BioStream Training or alternate game can produce feelings of frustration, anxiety, stress and fatigue including eye fatigue. These risks are no greater than those associated with minimal risk studies. As with any computer video game, seizure is a rare risk and possible SAE.

However, subjects are required to have played video games in the past and a history of seizures excludes participants from taking part in this study.

Psychological Stress and Anxiety: Due to the length of time associated with the assessments, some participants may experience fatigue, anxiety, or stress. Participants will be allowed to take breaks and stop at any time. Additionally, the presentation of unpleasant stimuli (including social interactions that are challenging for some youth with ASD) might be distressing to some participants. To minimize risk associated with the presentation of unpleasant stimuli, several precautions will be taken: (i) only members of the study team that are trained to conduct study visits by a Board Certified Behavior Analyst with experience in working with children with ASD, will conduct study visits, (ii) Parents/guardians will be shown examples of stimuli as part of the consent process and will be asked whether they feel confident that their child will not find these overly distressing, (iii) the parent/guardian or teacher or therapist (as applicable) will be instructed and agree to oversee gameplay to look for signs of distress in the subject and the tasks will be stopped if the subject appears distressed or requests to stop.

Risks Associated with Behavioral Data Collection: These risks are no greater than those associated with minimal risk studies.

Breach of Confidentiality: Confidentiality is carefully guarded to address issues of privacy and insurability. In particular, each subject is assigned a unique alphanumeric identifier immediately upon recruitment. Although a list linking the study number to the subject's name is maintained for future studies and contact, the name does not appear on any other document (other than Informed Consent Forms and Assent Forms). The families are informed of this link and are assured that only the PI has access to that list. The purpose of the list linking study ID number to the name is to record who we have already recruited so that we accidentally do not re-approach any family.

7.4.3 Potential Benefits of Trial Participation

There is no direct benefit to participation in this study, however it is possible that progress made during the training could be generalizable as a therapeutic benefit. Subjects will receive collateral benefits. We anticipate indirect benefits to the community of people with ASD at large. Researchers will be able to increase their understanding of the behavioral foundations of this disorder as well as the propensity of people with ASD towards specific game-like applications, which may be translated into improved future treatments. In addition, it could significantly advance development of an intervention and/or diagnostic tool to help children with ASD.

7.4.4 Risk-Benefit Assessment

It is hoped that the knowledge gained will indirectly benefit the participants as well as the larger community of people with ASD. The risks of the study procedures including the effects of behavioral measurements and assessments are all considered minimal risk.

7.5 Recruitment Strategy

In-home Subject Recruitment

With respect to members of the study team that have a therapy practice that includes in-home patients, in-school patients, or in-center patients, they will recruit from within their patient base for in-home study subjects.

Additionally, recruitment will occur through phone and in-person outreach by study team members to organizations that serve the needs of families of children with ASD to help identify families that may have an interest participating in the study. Such organizations will provide a study team member's contact information to those families that they, in their discretion, decide to contact that express an interest in learning more about the study. The study team will not receive the names or telephone numbers of potential study participants without their verbal consent to share that information.

Study team members may also engage in outreach through their personal and professional network of contacts to help identify families that may have an interest participating in the study. Such contacts will provide a study team member's contact information to those families that they, in their discretion, decide to contact that express an interest in learning more about the study. The study team will not receive the names or telephone numbers of potential study participants without their verbal consent to share that information.

In-school, and In-center Subject Recruitment

Schools, therapy centers, and research organizations that serve the needs of children with ASD or conduct research involving children with ASD will be approached by the Sponsor to source potential subjects. These organizations will approach parents of potential subjects and assess interest in the project and ask permission to connect to the study team. No additional subject information, excluding information collected in the ordinary course of operations, will be collected before this permission is given.

7.6 Informed Consent/Assent and HIPAA Authorization

After a thorough discussion of the study and its procedures, the parent/legal guardian will be consenting and giving permission for their child to participate in this study. Children ages 7 to 14 entering the study will give their assent to participate.

Initial Interview Phase. When a parent/legal guardian expresses interest in having their child participate in the study, an in-person meeting or telephone call will be set up by a member of the study team to review the study details, risks, benefits, financial considerations, and HIPAA procedures that are in place to insure privacy and confidentiality. The member of the study team will explain that an initial eligibility interview needs to be conducted as a first step, and they will be told that all information collected will be kept strictly confidential. The nature of the risks and benefits of participating in the screening interview will be explained. The parent/legal guardian will then undergo a short (up to 30 min) in-person or by phone screening interview to determine study eligibility. The specific inclusion or exclusion criteria in question will be described, and the parent/legal guardian will have an opportunity to ask questions. After the results of initial interview phase are received and evaluated, the parent/legal guardian will be contacted again with the results. The parent/legal guardian will be informed of specific inclusion or exclusion criteria that are not met/met based on this more detailed review.

In-Person Study Phase. After the initial interview phase, those parents/legal guardians of children that met the study inclusion and exclusion criteria in the initial interview phase and who are interested in participating in the study will be scheduled for have their first visit in the home, school, therapy center, or research organization (as applicable). Upon the study team member's arrival at the subject's home, school, therapy center, or research organization (as applicable), the first agenda item will be a face-to-face conversation with the parent/legal guardian to review the study protocol. The parent/legal guardian will then be asked to read the consent forms. Prior to signing the forms, the study team member will encourage the parent/legal guardian to ask as many questions as they wish, until they fully understand all aspects of the study, including its risks and benefits, as well as the time demands and inconveniences of study participation. This is critical, as it does not benefit the parent/legal guardian or the researchers to have a misunderstanding at this phase as to what full study participation entails. The study team member will also remind the parent/legal guardian that the subject's participation in the study is voluntary and that the parent/legal guardian or child can terminate participation at any time with no obligations to continue and no penalties whatsoever. Refusal to participate will in no way influence the individual's relationship with the study team member. In addition, if the participants' parent/legal guardian is an employee of the study team member's organization or Sponsor, they will be informed that their participation will not affect their performance evaluations or employment and that the study data will not be shared with their supervisor.

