Social Responsiveness Scale-Parent (SRS [19]): The SRS is a parent-report questionnaire that asks parents to rate the frequency of reciprocal social behaviors, communication, and repetitive and stereotypic behaviors in their child. The questionnaire yields a single summary score that can be used as an index of the child's severity of social deficits. This will be completed by a parent during each in-person visit or by telephone with a member of the study team.

Childhood Joint Attention Rating Scale (C-JARS [20]): This is a parent-report measure of joint attention related behaviors in verbal children and adolescents with ASD. This will be completed by a parent during each in-person visit or by telephone with a member of the study team.

Dyadic Interaction Task: There is a lack of standardized validated reference standards for assessing communication-based autism symptoms [21, 22]. Because of this, an exceptionally

large array of assessments is used in the literature. In fact, there are only three standardized tools that have been used in more than 2% of recent trials of autism interventions (none of which are used in more than 7% of studies) [21]. Therefore, in order to determine how we would assess communication skills we worked closely with our team of certified Applied Behavioral Analysis (ABA) therapists, who have years of experience working with children with ASD, and consulted the literature. The task we have constructed follows the Contextual Assessment of Social Skill [23] and procedures developed by Reilly et al [24]. It involves a structured play scenario, which is standard in other similar studies [21, 25-28].

This is an interaction between the subject and a member of the study team where the study team member poses questions to the subject while the interaction is video recorded. Questions may include but are not limited to the following:

What is your birthday? How old are you?
 What do you like to do at school? What do you like about ____?
 What is your least favorite thing at school?
 What do you like to do at home?
 Do you like any sports such as...?”
 Do you have any favorite movies? What’s [that movie] about?
 What’s your favorite program on TV? What’s [that show] about?

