2 STUDY OBJECTIVES

2.1 Primary Objective (or Aim)

The primary objective of this study is to determine whether 6.67 to 33.33 hours of BioStream Training improves the performance of children with ASD on social skills assessments including in comparison to an alternate game. Specifically with respect to the following:

The mean change from baseline score on the following assessments based on post-final game play session assessment compared to the alternate game group:

- a. Subject gaze patterns as measured by video eye tracking assessment.
- b. Subject gaze patterns as measured by the dyadic interaction task.
- c. Mean change in baseline score on the Ekman 60 Faces Test.
- d. Mean change in baseline score on the TOVA.
- e. Mean change in baseline score on the SRS.

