3.4.2 Exclusion Criteria

- 1) History of seizures.
- 2) History of traumatic brain injury or other significant medical or neurological abnormality affecting motor or higher cortical functioning. This includes gestational age below 32 weeks or perinatal injury, where the risk for brain injury is greatly increased. Rationale: a primary aim of the study is to identify sequences in our game-like applications that are appealing to youth with ASD; it is not clear that individuals with any type of acquired brain injury would provide useful data on what appeals to an individual with ASD.
- 3) A visual disorder that cannot be corrected through the use of corrective lenses to a level of 20-40 in both eyes.
- 4) Use of corrective visual lenses that would significantly impede the valid collection of visual attention and gaze pattern data during dyadic interaction tasks.
- 5) Auditory impairment (that cannot be corrected by a hearing aid) that would significantly impede the valid collection of test measures.
- 6) Profound intellectual disability or sensory-motor difficulties that would preclude valid use of diagnostic instruments and/or use of a computer or mobile computing device.
- 7) A DSM 5 disorder or other psychiatric symptoms that would interfere with the participant's ability to participate in the study (e.g., active psychosis), per parent report.
- 8) History of one or more psychiatric hospitalizations.
- 9) Presence of significant symptoms of a conduct disorder.

Subjects that do not meet all of the enrollment criteria may not be enrolled. Any violations of these criteria must be reported in accordance with IRB Policies and Procedures.

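### Children of Sponsor employees and study-team members are not excluded, so a parent with an interest in the product can rate the SRS (primary) and C-JARS (secondary)

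*Combined protocol and SAP*

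**What the plan says.** Protocol section 7.6 (In-Person Study Phase) deals with the case where the "parent/legal guardian is an employee of the study team member's organization or Sponsor". For these parents it gives two assurances: "they will be informed that their participation will not affect their performance evaluations or employment", and their supervisor will not see the data. Nothing is said about their role as raters.

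The eligibility lists in 3.4.1 and 3.4.2 contain no criterion on employment or financial interest. Section 3.4.2 closes with the rule "Subjects that do not meet all of the enrollment criteria may not be enrolled", but no listed criterion would exclude an employee's child. On recruitment, section 7.5 states: "Study team members may also engage in outreach through their personal and professional network of contacts". Section 7.3 counts Sponsor personnel among the study team.

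On the raters, section 1.4 states: "The SRS is a parent-report questionnaire that asks parents to rate the frequency of reciprocal social behaviors". Of the C-JARS it says: "This is a parent-report measure of joint attention related behaviors in verbal children and adolescents with ASD". Section 2.1 lists the SRS as primary endpoint (e), "Mean change in baseline score on the SRS". Section 2.2 lists the C-JARS as secondary endpoint (b).

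Section 3.2 has blinding in its title but describes only random assignment. The only people described as blinded are those who annotate the dyadic-task video (1.1, 1.4, 7.3). Section 5.7.2 analyses all randomised children with initial and final visit data. It has no flag or sensitivity analysis for employee families.

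**The concern.** Parent ratings are subjective. A parent who works for the Sponsor or sits on the study team has an interest in the result and is better placed than most to tell the training game from the alternate game. Such a parent could, without intending to, report fewer social difficulties after training, or see less improvement after the alternate game. Randomisation does not remove this bias, because it arises when the outcome is measured and its direction depends on the arm.

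The protocol recognises that these families may take part but treats only the employment side of the conflict. At stake is the between-arm comparison on one of five primary endpoints and one of two secondary endpoints. Even where the numerical effect is slight, a critic can easily attack a result that rests partly on ratings by the developer's own staff.

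**Working it through.** **Step 1: the text.** Each link was checked separately.

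| Link | Where | Finding |
|---|---|---|
| Employee parents foreseen | 7.6 | Yes, conditionally; safeguards cover employment and privacy only |
| Barred by eligibility | 3.4.1, 3.4.2 | No |
| Parent is the rater | 1.4, Tables 2 and 3 | Yes, SRS and C-JARS |
| Endpoint level | 2.1, 2.2 | SRS primary, C-JARS secondary |
| Parent masking | 3.2 | None described |
| Parent sees the game | 3.1.2, 7.4.2 | Home: parent is trained on the assigned game and oversees play. Elsewhere: a teacher or therapist may do both |
| Remedy in the analysis | 5.7.2 | None |

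**Step 2: possible size.** The plan gives no figure to reproduce: section 5.8 states up to 150 participants, with no power, SD or allocation ratio. The following is therefore an illustration.

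Assumptions: 150 children split 1:1, so 75 per arm; all contribute data; two-sided test, normal approximation; no true effect; *k* conflicted parents in each arm, each shifting the rating by *b* SDs of the change score in the product's favour, in both arms.

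- SE of the between-arm difference = √(2/75) = 0.163 SD
- Shift in the difference = 2*kb*/75
- Chance of a false favourable result = 1 − Φ(z − shift/SE), with z = 1.960 at α = 0.05, or 2.576 at α = 0.01 (Bonferroni over five primary endpoints, 0.05/5)

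Worked case, *k* = 4 and *b* = 1: shift = 8/75 = 0.107 SD; shift/SE = 0.653. At α = 0.05 this gives 1 − Φ(1.307) = 9.6%. At α = 0.01 it gives 1 − Φ(1.923) = 2.7%.

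| *k* per arm | Share of 150 children | Shift, *b* = 1 | α = 0.05, *b* = 1 | α = 0.01, *b* = 1 | α = 0.05, *b* = 0.5 | α = 0.01, *b* = 0.5 |
|---|---|---|---|---|---|---|
| 0 | 0% | 0 | 2.5% | 0.5% | 2.5% | 0.5% |
| 1 | 1.3% | 0.027 SD | 3.6% | 0.8% | 3.0% | 0.6% |
| 2 | 2.7% | 0.053 SD | 5.1% | 1.2% | 3.6% | 0.8% |
| 4 | 5.3% | 0.107 SD | 9.6% | 2.7% | 5.1% | 1.2% |
| 8 | 10.7% | 0.213 SD | 25.7% | 10.2% | 9.6% | 2.7% |

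If only training-arm parents shift, the shift halves: four such parents at 1 SD give 5.1% at α = 0.05.

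**Step 3: which α applies.** Sections 5.5 and 5.7.2 promise a correction across primary endpoints but do not name it, so Bonferroni is an assumption. No correction is stated for the C-JARS. The 2022 supplement adds mixed ANOVAs for the SRS and C-JARS at 0.05 and mentions no correction. The uncorrected columns are therefore relevant to the C-JARS and to those added analyses.

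**The case against.** The strongest reply is that section 7.6 is a conditional safeguard against coercion. It does not say that employee families are sought or expected, and no number is given. The network outreach in 7.5 works through contacts who decide whom to approach; it is not recruitment of staff. Eight conflicted parents per arm would mean 16 of 150 children, each with confirmed ASD, in the age range and under the Ekman ceiling. Nothing in the documents supports such a share, and the 25.7% figure also needs a full 1 SD shift in opposite directions in both arms and no multiplicity correction. All of this stands: the documents show an open route to bias, not a bias known to operate.

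Three stronger readings are tempting, and the documents do not support them.

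- A reader might infer that all these parents are unmasked. No section says that parents are told the arm. The inference is strong for home use and for Sponsor staff. It is weak at schools and centres, where the parent need attend only the first visit and may give later ratings by phone (4.2). The comparator may also be a modified version of the same product (1.2).
- A reader might infer that every employee parent has a stake in the product. That is clear for the Sponsor. For staff of a school, therapy center or research organization it is undocumented.
- A reader might infer that the trial's efficacy evidence as a whole is compromised. The other four primary endpoints are not parent-rated.

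It can also be said that the larger problem is parent-rated endpoints without described masking for all families. That is right. This subset nevertheless adds a conflict of interest, and it can be removed even if parents in general cannot be masked.

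**Conclusion.** The point holds as a low-severity, cheap improvement. The plan leaves open that a parent employed by the Sponsor or on the study team rates a primary and a secondary endpoint. No masking of that parent is described, and the analysis has no provision for it.

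The likely effect is small. One such parent per arm moves the false-favourable rate from 2.5% to about 3.6% uncorrected. Four per arm move it to about 9.6% uncorrected, or from 0.5% to about 2.7% with Bonferroni over five. These figures rest on 75 per arm, a 1 SD shift by each conflicted parent in both arms, and an assumed number of such families; a 0.5 SD shift gives much less. The direction of bias meant here is in the product's favour. Because the SRS score indexes severity of social deficits, that means lower SRS scores in the training arm and higher ones in the control arm.

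**What to change.** Add one criterion to section 3.4.2, mirrored in the synopsis: exclude a child whose parent, guardian or household member is employed by the Sponsor, has a financial interest in it, or is a member of the study team.

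For parents employed by a site organisation but not on the study team, whose stake is undocumented, exclusion is not warranted. Record the employment on the case report form, and pre-specify in section 5.7.2 a repeat of the SRS and C-JARS comparisons without those children.

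The cost is one eligibility line, one check box and one sensitivity analysis, plus the loss of a few easily recruited children. Section 3.3.1 planned enrolment to end in February 2020, so the exclusion would help only any further enrolment. The 2022 supplement still describes the SRS and C-JARS analyses as to be done, so the repeat analysis, leaving out Sponsor-linked and study-team families as well, could be specified there if employment status can be established. The documents do not require it to be recorded.

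None of this replaces a statement in section 3.2 of whether parents are masked. That wider gap needs its own answer.
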